10.5 Personal Data breaches

Personal data breaches will be immediately reported to the UCL Information Security Group (ISG) and the UCL Data Protection Officer [name] ([contact]), and to the Sponsor via the [UCL JRO research incident reporting form](#) (as per form and guidance: <https://www.ucl.ac.uk/legal-services/guidance/reporting-loss-personal-data>). The following information will be provided: full details as to the nature of the breach, an indication as to the volume of material involved, and the sensitivity of the breach (and any timeframes that apply). Sites will additionally follow their Trust incident reporting mechanisms, and will document this within their TMF/ISFs.

11. STATISTICAL CONSIDERATIONS

11.1 Primary outcome

Compulsory readmission measured at 12-months.

11.2 Sample size calculation

We will aim to recruit eighty participants in line with recommendations by Consolidated Standards of Reporting Trials (CONSORT) for pilot RCTs (Eldridge et al. 2016), forty of which will be randomly allocated to the therapy arm and forty to the TAU arm. A sample of eighty is deemed of sufficient

size to examine the aims of the study. Data (for example, relevant proportions, means standard deviations and confidence intervals) from this study will be used to inform a power calculation for a future, definitive, fully powered effectiveness trial.

11.3 Planned recruitment rate

Baseline recruitment will be conducted from January 2022 to September 2022 with an estimated 10 participants recruited per month.

11.4 Randomisation methods

Randomisation will take place following baseline interviews. An independent statistician at University College London will allocate participants via a computer-generated allocation sequence to either the intervention or control group in a 1:1 ratio using block randomisation stratified by site and ethnicity (ethnic minority groups at higher risk of detention vs White/Other).

11.5 Statistical analysis

11.5.1 Clinical outcome analysis

The study will follow best practice guidance for the reporting of pilot RCTs (CONSORT, Schulz, Altman & Moher, 2010; Eldridge et al., 2016). The focus of the analysis will be on key indicators of feasibility, including participant recruitment, retention and acceptability of the intervention, which will be summarised descriptively using frequencies and percentages. Continuous clinical outcome measures will be summarised separately by study arm using means and standard deviations or medians and interquartile ranges, as appropriate for the distribution of the data. Binary outcome measures will be summarised using frequencies and percentages. The quantity of missing data for each clinical outcome will be examined and likewise summarised by study arm. This pilot study will not have sufficient statistical power to assess the effectiveness of the intervention, although it will allow an assessment of whether the direction and magnitude of any effect found for the proposed primary outcome are consistent with a hypothesis that the programme is effective in reducing repeat detentions. For this reason and to test the analysis envisaged for a future, fully powered, effectiveness RCT, clinical outcomes at follow-up time points will be compared between study arms, using linear or logistic regression models as appropriate, and adjusting for the baseline measure of the outcome in question.

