5. SAMPLING METHODS

Participants will be recruited from three sites; Camden & Islington NHS Foundation Trust, North East London NHS Foundation Trust, and Lancashire and South Cumbria NHS Trust. Purposive sampling will be undertaken to ensure that the sample is representative of the service user population. We will aim for half of our participants to be from ethnic minority groups at higher likelihood of being admitted (i.e those from Black, Asian and mixed-race ethnic minority backgrounds).

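### Randomisation is stratified by site and ethnicity, but the stated between-arm models adjust only for the baseline measure, so linear-model intervals are too wide if either factor predicts outcome

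*Protocol*

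**What the plan says.** Section 11.4 of the protocol specifies "block randomisation stratified by site and ethnicity (ethnic minority groups at higher risk of detention vs White/Other". The study summary and sections 4.2 and 8.2 say the same. Section 5 gives the number of sites ("Participants will be recruited from three sites") and the ethnicity target ("We will aim for half of our participants to be from ethnic minority groups at higher likelihood of being admitted"). That makes 3 × 2 = 6 strata, split roughly evenly by ethnicity if the target is met.

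Section 11.5.1 describes the comparison of arms: "clinical outcomes at follow-up time points will be compared between study arms, using linear or logistic regression models as appropriate", "adjusting for the baseline measure of the outcome in question". The statistical paragraph of the study summary repeats this covariate. Neither place mentions site or ethnicity.

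Section 11.5.1 also gives the standing of these models: "This pilot study will not have sufficient statistical power to assess the effectiveness of the intervention". They are there to try out the analysis intended for the definitive trial, and to see whether the direction and size of effect fit the hypothesis of benefit.

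For the primary outcome, section 8.1.1 defines the pre-intervention value as whether the participant had been compulsorily detained. Section 5.1.1 makes detention in the current admission an entry criterion.

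**The concern.** Stratified blocks make the arms nearly alike on site and ethnicity. Differences between strata therefore add almost nothing to the true variance of the treatment estimate. A linear model without those factors still counts the differences as residual error. If the factors predict outcome, the reported standard error exceeds the true one and the interval is wider than it should be.

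The protocol gives some reason to expect this for ethnicity. Section 2 reports that Black and Black British people are around four times as likely to be detained as White British people, and the stratum is defined by detention risk.

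What is at stake is mainly the rehearsal. The models are meant to try out the definitive analysis, and section 11.2 lists confidence intervals among the data that will inform the later power calculation. For readmission, the single named covariate can do no work, so the stratification factors are the obvious ones to name.

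**Working it through.** **Inputs from the protocol.** 80 participants ("forty of which will be randomly allocated to the therapy arm and forty to the TAU arm"), three sites, two ethnicity levels with a target of half in each, 1:1 stratified blocks, and linear or logistic models with baseline as covariate. Section 11.2 states no alpha, power or effect size, so there is no power figure to reproduce. For context, 40 per arm has about 29% power for 43% versus 28% (the two-year rates quoted in section 2), and 80% power would need 159 per arm. This agrees with the protocol's statement that it is underpowered.

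**Inputs that are assumed.** Block size 4, and the prognostic strength of the strata. The protocol gives neither, so a range of strengths is shown.

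**Closed-form check, linear model.** Let the residual variance given baseline be 1, with share R² due to strata. Without the strata terms, the reported SE is about 2/√80 = 0.224 whatever R² is. With near-perfect balance, the true SD of the estimate is about 2√(1 − R²)/√80. The ratio is 1/√(1 − R²): 1.026 at 5%, 1.054 at 10% and 1.118 at 20%. Incomplete blocks leave a little imbalance, so the actual ratio should be slightly smaller.

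**Simulation, linear model.** No treatment effect, 10,000 trials per row.

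| Strata share of residual variance | Stated model: mean SE | True SD | Ratio | 95% CI coverage | Coverage with site and ethnicity added |
|---|---|---|---|---|---|
| 0% | 0.224 | 0.224 | 1.00 | 95.1% | 95.3% |
| 5% | 0.225 | 0.220 | 1.02 | 95.4% | 94.9% |
| 10% | 0.224 | 0.214 | 1.05 | 96.0% | 95.0% |
| 20% | 0.224 | 0.202 | 1.11 | 97.0% | 94.9% |
| 30% | 0.225 | 0.191 | 1.18 | 97.9% | 95.1% |

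A repeat simulation put the 20% row nearer 10%. With the factors added, mean SE and true SD agree, for example 0.213 and 0.214 at 10%.

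**Expected readmissions at 12 months.** Assume a constant hazard and the earlier trial's two-year rates of 28% and 43%. One-year risks are 1 − √0.72 = 0.151 and 1 − √0.57 = 0.245. Expected events are 40 × (0.151 + 0.245) = 15.8, about 16.

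**Simulation, logistic model.** At a 43% event rate, with stratum log-odds SD of 0, 0.35, 0.7 and 1.0, the unadjusted mean SE is 0.458 against true SDs of 0.468, 0.463, 0.446 and 0.425. Coverage is 94.6%, 94.5%, 95.6% and 96.8%. Adding site and ethnicity raises the mean SE to 0.469–0.523, because the adjusted odds ratio is a conditional quantity. Coverage is then 94.2–95.1%. At a base rate near 20% (16–19 events), the unadjusted SE is not overstated until the strata are very strong, and then by about 2% (0.539 against 0.526). Ordinary adjusted logistic regression failed or gave unusable SEs in about 1–5% of runs.

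**Baseline covariate for readmission.** Under section 8.1.1 it records detention or not, and under section 5.1.1 every participant has been detained. The covariate takes one value, so its coefficient cannot be estimated and the model reduces to treatment alone.

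**The case against.** The case for leaving the plan alone has four parts.

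- **The SAP may settle it.** Full covariate lists often sit in an SAP, section 22.1 lists SAPs as an output, and section 11.5.1 does not say that baseline is the only covariate. This has some force. But the protocol does not leave the covariate open: it names one, twice, and omits both stratification factors. An SAP that adds them would go beyond the stated model.
- **The error is conditional and cautious.** A reader might infer that the standard errors are wrong for this design whatever the data, or that the estimate is biased or the type I error inflated. The documents do not support this. With non-prognostic strata the linear SE is correct. With prognostic strata the interval is too wide and the test size falls below 5%.
- **Little rests on these intervals.** The focus is descriptive feasibility, the progression thresholds concern recruitment, retention and delivery, and arm proportions and SDs for a later power calculation need not come from these models. This stands, and it limits the point to the rehearsal of the analysis.
- **Readmission is different.** A reader might infer that adjustment would also narrow the readmission odds ratio interval. It would not, as shown above, and with few events ordinary adjustment may not fit.

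A reader might also infer that both factors were chosen because detention risk differs by them. No section says this of site. For ethnicity, the four-fold figure concerns detention in general, not readmission among people already detained.

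**Conclusion.** The mismatch is real and modest. The stated covariate set omits both factors that restrict the randomisation. The linear-model SE is then too large by 0% to about 10–11% as the strata explain 0% to 20% of residual variance, with coverage of up to 97%, and adding the factors restores about 95%. This rests on assumed prognostic strength and an assumed block size of 4.

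The treatment estimate and the feasibility conclusions are unaffected. For readmission, the gain in precision is on the risk-difference scale, and the clearer defect is a named covariate that cannot vary on the section 8.1.1 definition. The expectation of about 16 events assumes a constant hazard and the earlier trial's rates. The case for change is that these models are meant to be the template for the definitive trial.

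**What to change.** In section 11.5.1 and the study summary, state that every between-arm model includes site and the ethnicity stratum as fixed effects, plus the baseline measure of the outcome where it varies between participants. If the sponsor prefers to leave the factors out, give the reason.

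For compulsory readmission, name a method suited to few events: either a risk difference adjusted for site and ethnicity, such as Mantel-Haenszel, or Firth-penalised logistic regression. If Mantel-Haenszel is used, name a variance estimator meant for sparse strata, such as Sato's, because 80/6 is only about 13 participants per stratum. State also that no baseline term is fitted for this outcome, or define one that varies.

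The cost is a few sentences. Site and ethnicity are known at randomisation, so nothing new is collected. The downside is three extra parameters (two for site, one for ethnicity), which hardly matters for linear models with 80 participants and is why readmission needs its own method.

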Main inclusion/exclusion criteria:	Eligible patient participants will: have been compulsorily detained during their current hospital admission; be due to receive community mental health care locally post-discharge; be aged 18 and over; have capacity to consent at the time of recruitment. They will be recruited close to the point of discharge.
Statistical methodology and analysis:	
Quantitative analysis: The focus of the analysis will be on key indicators of feasibility, including participant recruitment, retention in the trial and the intervention, which will be summarised descriptively using frequencies and percentages. Continuous clinical outcome measures will be summarised separately by study arm using means and standard deviations or medians and interquartile ranges, as appropriate for the distribution of the data. Binary outcome measures will be summarised using frequencies and percentages. The quantity of missing data for each clinical outcome will be examined and likewise summarised by study arm. This pilot study will not have sufficient power to assess the effectiveness of the intervention. However, to trial the analysis envisaged for a future, fully powered, effectiveness RCT, clinical outcomes at follow-up time points will be compared between study arms, using linear or logistic regression models as appropriate, and adjusting for the baseline measure of the outcome in question.

	
Qualitative analysis: Semi-structured interviews will be transcribed verbatim and analysed using thematic analysis. Analysis will be conducted on NVivo software. Initially each transcript will be read and reread to ensure the researcher is fully immersed in the data, and then initially coded. Codes will be collated together across interviews and grouped together to form analytical themes. Patterns of themes will be explored across the data set focussing on both commonalities and variations and comparing service user and therapist perspectives. The theme structure will be checked with a small number of participants to check it reflects their experiences. The final theme structure will also be discussed with the research team and stakeholder group (including people with lived experience of psychosis and inpatient admission).

FUNDING & OTHER	
Funding	National Institute of Health Research
STORAGE of SAMPLES / DATA (if applicable)	
Data collected / Storage	[name], Division of Psychiatry, [name]
KEY STUDY CONTACTS	

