8.4.2. Primary outcome

Compulsory readmission to hospital will be examined at 12-months and 24-months. These data will be taken from the participants' medical notes.

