8.4.3. Secondary outcome measures

All secondary clinical outcomes outlined in section 7.1 will be repeated six months post randomisation and twelve months post randomisation. These will be conducted either face to face or remotely.

Service engagement and service use will be collected from medical records at 12 and 24 months.

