8.5 Discontinuation/withdrawal of participants

In consenting to participate in the trial, participants are consenting to intervention, assessments, follow-up and data collection. Participants also consent to the research team continuing to collect data from medical records should they lose capacity at any point during the trial.

Therefore, if a participant loses capacity during the course of the trial, they will no longer be contacted for follow-up assessments. However, their data collected up until that point will be retained and the study team will continue to use data from the participant's medical records.

However, if within a month clinicians judge capacity to have returned, and if participants wish to continue with research assessments, we will try to include the participant again at this stage. If more than a month elapses without a clinician indicating the participant has capacity to continue, we will assume capacity has been lost and stop contacting participants about further research assessments.

We make these allowances because transient relapses are fairly frequent amongst populations of individuals with Serious Mental Illness and we would like to provide the participants the opportunity to fully re-enter the study should they wish.

8.6 If a participant explicitly states they do not wish to contribute further data to the trial their decision must be respected and recorded in the CRF and medical notes.

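### For the continuous interview outcomes, the 12-month comparison adjusts for baseline only and leaves the 6-month score unused; a model of both visits would protect better against relapse-related loss at little cost.

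*Protocol*

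**What the plan says.** Section 11.5.1 states the model: "clinical outcomes at follow-up time points will be compared between study arms, using linear or logistic regression models as appropriate", "adjusting for the baseline measure of the outcome in question". The Study Summary, under statistical methodology, repeats it. No repeated-measures model is named, and the 6-month value is not listed as a covariate for the 12-month comparison.

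Section 8.4.3 says that the secondary clinical measures "will be repeated six months post randomisation and twelve months post randomisation", and Appendix 1 marks the interview measures at both visits. The primary outcome is different: "Compulsory readmission to hospital will be examined at 12-months and 24-months", from medical notes, with no 6-month value and (in the section on trial parameters) a follow-up goal of at least 90%.

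On missing data, section 11.5.1 says only this: "The quantity of missing data for each clinical outcome will be examined and likewise summarised by study arm". How missing values enter the model is not stated.

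Section 8.5 says of participants who lose capacity that "they will no longer be contacted for follow-up assessments". They may return if clinicians judge within a month that capacity has come back; otherwise contact about research assessments ends. Collection from records continues.

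**The concern.** Each continuous interview outcome has a 6-month score that is likely to predict both the 12-month score and whether a 12-month interview takes place. A 12-month regression on arm and baseline ignores it. On available cases, that regression is unbiased if loss depends only on arm and baseline. Section 8.5 makes a further dependence plausible, because it ties missing interviews to loss of capacity and gives the frequency of short relapses as the reason for its re-entry rule. If the intervention prevents crises, more controls than intervention participants could be lost in this way. The background section adds that unequal drop-out clouded the result of the earlier Swiss trial.

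What is at stake is modest but real. Section 11.5.1 presents the comparison as a rehearsal of the analysis for the definitive trial, and section 11.2 says that pilot estimates will inform its power calculation. A model that is sensitive to the expected kind of loss would be carried forward.

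**Working it through.** **Inputs from the protocol.** 40 per arm (section 11.2); visits at baseline, 6 and 12 months (section 8.4.3); regression on arm and baseline (section 11.5.1). The protocol gives no interview attrition rate, correlation or expected effect on these scores, so there is no figure of its own to reproduce.

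**Assumptions.** Scores have SD 1, and higher is better. Correlations are 0.5 (baseline to 6 months), 0.4 (baseline to 12 months) and 0.6 (6 to 12 months). Loss rates are varied. Where loss depends on a score, low scorers are more likely to be lost (logistic slope 1.5 per SD), except in the opposite-directions row.

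**Why the 6-month score matters.** Given baseline, the coefficient of the 6-month score in predicting the 12-month score is

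(0.6 − 0.5 × 0.4) / (1 − 0.5²) = 0.40 / 0.75 = 0.53.

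To a close approximation, the bias of the available-case regression is 0.53 × (shift in intervention arm − shift in control arm). Each shift is how far the completers' mean 6-month score, given baseline, has moved through selection. If loss is unrelated to that score, both shifts are zero. If the dependence and the loss rate are the same in both arms, the shifts cancel. They differ if low scorers are lost and one arm loses more of them.

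**Simulation with no true effect** (4,000 trials per row). Entries are the bias of the 12-month difference in SD units. The second estimate combines the 6-month comparison with the 12-month regression on arm, baseline and 6-month score, which is how a joint likelihood model uses the data.

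| Loss depends on | Control / intervention loss | Baseline-adjusted regression | Using the 6-month score |
|---|---|---|---|
| nothing but arm | 40% / 20% | 0.00 | 0.00 |
| baseline score | 40% / 20% | 0.01 | 0.01 |
| 6-month score, same in both arms | 20% / 20% | 0.00 | 0.00 |
| 6-month score, same in both arms | 30% / 15% | −0.06 | 0.00 |
| 6-month score, same in both arms | 40% / 20% | −0.08 | 0.00 |
| as above, 80% of those lost also lack the 6-month score | 40% / 20% | −0.08 | −0.05 |
| unseen 12-month score | 40% / 20% | −0.17 | −0.14 |
| 6-month score, opposite directions by arm | 40% / 20% | −0.29 | 0.00 |

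The sampling SD of one trial's estimate was about 0.22 to 0.27. Simulation error in each mean is about 0.25 / √4000 = 0.004.

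**With a true effect of 0.40 SD** and the same dependence in both arms:

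- 30% loss in each arm: about 0.40, so no material bias.
- 40% control and 20% intervention loss: 0.40 − 0.08 = about 0.32, a shortfall of 0.08 / 0.40 = 20%. Using the 6-month score restores 0.40.
- The same, with most of those lost also lacking the 6-month score: about 0.35 using the available 6-month scores, against 0.32 without them.

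The figures for 0.40 SD came out the same when re-run with the loss rates set exactly. A weaker dependence on the 6-month score gives a smaller bias.

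**Precision.** The gain is small. With 40% and 20% loss unrelated to outcome, the sampling SD falls from 0.252 to 0.243, which is 1 − 0.243 / 0.252 = 3.6%.

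**The case against.** The strongest reply is that missing-data handling belongs in the SAP, which is not at hand. Imputation using the 6-month score would be compatible with section 11.5.1 as worded. This stands against any claim that the protocol drops people without a 12-month interview: a reader might infer that, but the text does not say it. It does not dispose of the point, because the model and its covariate are stated in the protocol and the proposal is to replace that model.

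Second, a reader might infer that unequal attrition by itself biases the comparison. It does not, as the first two rows of the table show. Nor do the documents support errors of around 30%. In simulation those need loss driven by the 6-month score in one arm only, and the capacity rule in section 8.5 is the same for both arms.

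Third, that same rule can remove people before month 6, and then there is no 6-month score to use. This also stands, and it limits the remedy.

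Fourth, the protocol says "This pilot study will not have sufficient statistical power to assess the effectiveness of the intervention", the focus is feasibility, and patterns of attrition are themselves a feasibility outcome (section 8.4.1). Regression at each visit adjusted for baseline is also conventional. All this lowers the weight of the point. It does not justify rehearsing the less robust of two easy analyses.

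**Conclusion.** The point holds as a low-cost improvement, limited to the continuous interview outcomes. It is not a demonstrated bias. The stated 12-month model leaves the 6-month score unused, and on available cases it is open to bias if loss depends on that score beyond arm and baseline. With the same dependence in both arms, the bias ranges from none at equal loss rates to about 0.08 SD on a true 0.40 SD at 40% against 20% loss. That is roughly a third of the sampling SD (0.08 / 0.25). Larger values need arm-specific mechanisms, or loss driven by the unseen 12-month state, which the joint model would correct only slightly. Every correlation, loss rate and mechanism here is an assumption.

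A reader might extend the point to compulsory readmission. The documents do not support that: it comes from medical notes, has no 6-month value and does not depend on an interview. The Swiss drop-out mentioned in the background concerns a readmission result and comes without rates, so it says nothing about the size of loss in the interview scores.

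**What to change.** In section 11.5.1 and the Study Summary, replace the per-visit regression for continuous interview outcomes with one linear mixed model for repeated measures. It is fitted to the 6- and 12-month scores, with arm, time, arm-by-time and baseline score as fixed effects and an unstructured covariance (two variances and one covariance). Report the 6- and 12-month contrasts with confidence intervals. Keep the baseline-adjusted regression at each visit as a sensitivity analysis. Leave the analysis of compulsory readmission as it is.

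The cost is a few lines of text and code, with no new data. The model assumes that scores are missing at random given the observed ones. It reduces bias only in part when the 6-month score is also missing or when loss depends on the unobserved 12-month state. Reporting how many participants without a 12-month interview have a 6-month score, by arm, would show how much the model can recover.
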